9.5.4.4 Expedited Reporting

The sponsor must inform investigators and regulatory authorities of reportable events, in compliance with applicable regulatory requirements, on an expedited basis (ie, within specific time frames). For this reason, it is imperative that sites provide complete SAE information in the manner described above.

9.5.4.5 Breaking the Blind

In the case of a medical emergency where the appropriate treatment of the subject requires knowledge of the study treatment given, the investigator may break the randomization code for an individual subject. In all such cases, the AE necessitating the emergency blind break will be handled as an SAE in accordance with the procedures indicated above. Any broken code will be clearly justified and documented. The medical monitor must be notified immediately of the blind break.

9.5.4.6 Regulatory Reporting of Adverse Events

Adverse events will be reported by the sponsor or a third party acting on behalf of the sponsor to regulatory authorities in compliance with local and regional law and established guidance. The format of these reports will be dictated by the local and regional requirements.

9.5.5 Completion/Discontinuation of Subjects

The investigator may withdraw the subject from the study at any time for safety or administrative reasons. A subject may elect to discontinue the study at any time for any reason. All subjects will continue in the study until the 52-week evaluation is completed. Subjects who discontinue study drug prematurely will continue to be evaluated on for all study assessments until study completion. All attempts will be made to capture height and weight in all subjects whether or not they are still on IP at the end of the study. All subjects who discontinue the study are to complete the study's early discontinuation procedures indicated in the Schedule of Procedures/Assessments [Table 2](#)). (revised per Amendment 03)

The investigator will promptly explain to the subject involved that the study will be discontinued for that subject and provide appropriate medical treatment and other necessary measures for the subject. A subject who has ceased to return for visits will be contacted by

mail, phone, or other means to gather information such as the reason for failure to return, the status of treatment compliance, the presence or absence of AEs, and clinical courses of signs and symptoms.

Subjects who discontinue early from the study will be discontinued for 1 of these primary reasons: AE(s), lost to follow-up, subject choice, withdrawal of consent, pregnancy, study terminated by sponsor, or other. In addition to the primary reason, the subject may indicate 1 or more of the secondary reasons for discontinuation. Study disposition information will be collected on the Subject Disposition CRF. If “lost to follow-up” is recorded in clinical data base, appropriate queries will be sent to investigators in order to collect all the relevant reasons for missing data. (revised per Amendment 03)

Every effort, including proper training of all study participants and their parent/guardian, should be made in order to achieve optimal subject retention and prevent missing data, especially for the Week 52 primary endpoint. A retention plan to help avoid missing data will be developed and included in study manual. (revised per Amendment 03)

A subject removed from the study for any reason may not be replaced.

9.5.6 Abuse or Diversion of Study Drug

During the study, the investigator will report any concern about abuse or diversion of study drugs by completing the Abuse or Diversion of Study Drug CRF. The DEA Registrant has the responsibility to comply with local, state, and Federal laws to notify the Field Division Office of the DEA of any theft or significant loss of any controlled substances upon discovery of such theft or loss.

9.5.7 Confirmation of Medical Care by Another Physician

The investigator will instruct subjects to inform site personnel when they are planning to receive medical care by another physician. At each visit, the investigator will ask the subject whether he or she has received medical care by another physician since the last visit or is planning to do so in the future. When the subject is going to receive medical care by another physician, the investigator, with the consent of the subject, will inform the other physician that the subject is participating in the clinical study.

9.6 Data Quality Assurance

This study will be organized, performed, and reported in compliance with the protocol, SOPs, working practice documents, and applicable regulations and guidelines. Site audits will be made periodically by the sponsor’s or the CRO’s qualified compliance auditing team, which is an independent function from the study team responsible for conduct of the study.

9.6.1 Data Collection

Data required by the protocol will be collected on the CRFs and entered into a validated data management system that is compliant with all regulatory requirements. As defined by ICH

guidelines, the CRF is a printed, optical, or electronic document designed to record all of the protocol-required information to be reported to the sponsor on each study subject.

Data collection on the CRF must follow the instructions described in the CRF Completion Guidelines. The investigator has ultimate responsibility for the collection and reporting of all clinical data entered on the CRF. The investigator or designee as identified on Form FDA 1572 must sign the completed CRF to attest to its accuracy, authenticity, and completeness.

Completed, original CRFs are the sole property of Eisai and should not be made available in any form to third parties without written permission from Eisai, except for authorized representatives of Eisai or appropriate regulatory authorities.

9.6.2 Clinical Data Management

All software applications used in the collection of data will be properly validated following standard computer system validation that is compliant with all regulatory requirements. All data, both CRF and external data (eg, laboratory data), will be entered into a clinical system.

9.7 Statistical Methods

All statistical analyses will be performed by the sponsor or designee after the study is completed and the database is locked and released for unblinding. Statistical analyses will be performed using WinNonlin and SAS software or other validated statistical software as required. Details of the statistical analyses will be included in a separate statistical analysis plan (SAP).

9.7.1 Statistical and Analytical Plans

The statistical analyses of study data are described in this section. Further details of the analytical plan will be provided in the SAP, which will be finalized before database lock and treatment unblinding.

9.7.1.1 Study Endpoints

9.7.1.1.1 PRIMARY EFFICACY ENDPOINT

- Change in BMI from Baseline to Week 52

9.7.1.1.2 SECONDARY EFFICACY ENDPOINTS

KEY SECONDARY ENDPOINT

- Proportion (%) of subjects achieving at least a 5% BMI reduction at Week 52

OTHER SECONDARY ENDPOINT

- Proportion (%) of subjects achieving at least a 5% BMI reduction at Week 12

- Proportion (%) of subjects achieving at least a 10% BMI reduction at Week 52
- Percentage change in BMI from Baseline to Week 52
- Association between change and percentage change in BMI from Baseline to Week 52 with the outcome of achieving at least a 5% BMI reduction at Week 12 (revised per Amendment 02)
- Association between the proportion (%) of subjects achieving at least a 5% or 10% BMI reduction at Week 52 with the outcome of achieving at least a 5% BMI reduction at Week 12 (revised per Amendment 02)
- Change in waist circumference from Baseline to Week 52
- Change in total body composition (total fat and lean mass) in a subset of randomized subjects at end of 52 weeks of treatment (revised per Amendment 03)
- Change in HbA_{1c} from Baseline to Week 52 for subjects with Type 2 diabetes at baseline (revised per Amendment 03)
- Change in fasting glucose, fasting insulin, and HOMA-IR from Baseline to Week 52 for subjects with Type 2 diabetes at baseline (revised per Amendment 03)
- Change in fasting glucose, fasting insulin, and HOMA-IR from Baseline to Week 52 for the subjects without Type 2 diabetes at baseline (revised per Amendment 03)
- Change in BP (systolic and diastolic) and heart rate from Baseline to Week 52
- Change in fasting lipid profile (total cholesterol, LDL cholesterol, HDL cholesterol, triglycerides) from Baseline to Week 52
- Proportion (%) of subjects with prehypertension or primary hypertension at Week 52
- Proportion (%) of subjects with dyslipidemia at Week 52
- Subject compliance rate at each visit by pill count during 52 weeks of treatment (per Amendment 03)

9.7.1.2 Definitions of Analysis Sets

- The Safety Analysis Set is the group of subjects who received at least 1 dose of study drug and had at least 1 postdose safety assessment.
- The Full Analysis Set (FAS) is the group of all randomized subjects regardless of adherence to study drug.

- Per-Protocol Analysis Set (PP) is the group of all randomized subjects who are 80% or greater compliant with study medication, completed the study, have no major protocol deviations, have no violations of inclusion or exclusion criteria, and have BMI data at Baseline and Week 52. The determination of subjects to be excluded from this population based on the above criteria and list of major protocol violations will be included in the SAP and finalized before data base lock.
- The PD Analysis Set is the group of subjects who had sufficient PD data to derive at least 1 PD parameter.
- The PK Analysis Set is the group of all randomized subjects from whom at least 1 valid lorcaserin plasma concentration was obtained with associated documented dosing history.
- The population PK/PD set is the group of randomized subjects with PK information and who have at least 1 adequately documented measurement of BMI.

9.7.1.3 Subject Disposition

The number of subjects screened and the number (percentage) of subjects who failed screening and the reasons for screen failure will be summarized, based on data reported on the CRF.

For study completion, the number (percentage) of treated subjects who completed study treatment and who discontinued from study treatment will be summarized according to the primary reason for discontinuation and also according to secondary reason(s) for discontinuation, based on data reported on the CRF. The number (percentage) will be presented by treatment. The reasons for discontinuation from study treatment will be documented in the CRF and source documentation.

9.7.1.4 Demographic and Other Baseline Characteristics

Demographic and other baseline characteristics for the FAS and Safety Analysis Sets will be summarized for each treatment group using descriptive statistics or frequency count. Continuous demographic and baseline variables include age, height, BMI, waist circumference, and weight; categorical variables include sex and race.

9.7.1.5 Prior and Concomitant Therapy

All investigator terms for medications recorded in the CRF will be coded to an 11-digit character code using the World Health Organization Drug Dictionary. The number (percentage) of subjects who took prior and concomitant medications will be summarized for the Safety Analysis Set by treatment group, Anatomical Therapeutic Chemical class, and World Health Organization Drug Dictionary preferred term (PT). Prior medications will be defined as medications that stopped before the first dose of study drug. Concomitant medications will be defined as medications that started on or after the date of the dosing of study drug and continued up to 30 days afterward.

9.7.1.6 Efficacy Analyses

The FAS will be used as the primary analysis set for all efficacy analyses, while the PP will be used as a supportive analysis. Unless specified otherwise, a 2-sided $\alpha=0.05$ significance level will be used for all efficacy analyses.

Primary Efficacy Analysis

The primary efficacy endpoint is the change in BMI from Baseline to Week 52. The change from baseline in BMI will be analyzed using analysis of covariance model (ANCOVA) with factors of treatment, sex (male and female) as fixed effect, and the baseline age and BMI as covariates. The missing values will be imputed using a pattern mixture model utilizing multiple imputation (MI) assuming the missing values are missing not at random (MNAR). The missing values will be imputed at each visit using all available values including the retrieved measurement from the postdiscontinuation data. The details of the analysis model and missing value imputation method will be further described in the SAP.

In addition, the following analyses will also be considered as sensitivity analyses:

- PP analysis: The same primary efficacy analyses described above will be repeated based on the PP.
- Change from baseline in standardized BMI score (Z-score): The same primary efficacy analyses described above will be repeated using Z-score.

Subgroup analyses and additional sensitivity analyses, if appropriate, may also be performed and will be described in the SAP.

Key Secondary Efficacy Analysis

The key secondary efficacy endpoint is the proportion of subjects achieving at least a 5% BMI reduction at Week 52. The secondary efficacy endpoint will be analyzed only if the test for the primary efficacy endpoint is statistically significant.

The proportion of subjects achieving at least a 5% BMI reduction at Week 52 will be analyzed using a logistic regression model with factors of treatment, and sex (male and female), and baseline BMI as a covariate using FAS. Subjects with any missing assessment at Week 52 will be considered as treatment failures in this analysis.

Other Secondary Efficacy Analyses

Unless specified, for all other secondary efficacy endpoints, the continuous variables will be analyzed using mixed effect model repeated measurement analysis (MMRM) on the FAS for study treatment compared to placebo, as appropriate. The model will include all data and will include treatment, time, and the interaction of treatment by time as fixed effects, with adjustment for sex (male versus female), BMI and age at baseline, and subject as a random effect. (revised per Amendment 03)

Treatment by time interaction will be used to construct the treatment comparisons at a specific time. The MMRM model assumes that the missing data are missing at random and

makes use of all available data even if a subject has missing data at some post-baseline visits. An unstructured covariance matrix will be used, and if the model fails to converge, then an autoregressive matrix will be used. (revised per Amendment 03)

Categorical variables will be analyzed using the Cochran Mantel Haenszel test, Chi-square test, or logistic regression as appropriate. Additional analysis may be performed as needed using appropriate statistical methodologies as specified in SAP.

Subgroup analyses will be performed on the primary efficacy endpoint, including sex (male and female), race (American Indian or Alaska Native, Asian, Black or African American, Native Hawaiian or other Pacific Islander, or White), and age. Additional subgroups may be explored, if deemed necessary. (revised per Amendment 03)

No adjustment for multiplicity is planned for other secondary endpoints, subgroup, and sensitivity analyses.

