9 INVESTIGATIONAL PLAN

9.1 Overall Study Design and Plan

This is a multicenter, randomized, double-blind, placebo-controlled, parallel-group study in obese adolescents ages 12 to 17 years. Approximately 260 subjects will be randomized in a 1:1 ratio to Belviq XR 20 mg QD (130 subjects) and placebo (130 subjects). Subjects will be stratified by sex. Subjects will receive Belviq XR 20 mg or matched placebo QD in a 1:1 ratio for up to 52 weeks. A recruitment plan will be developed to ensure at least 20% of younger subjects (12 to 13 years of age) are enrolled in the study. Throughout the duration of the study, subjects will be encouraged to adhere to a lifestyle modification program that includes a standardized, age-appropriate diet and exercise counseling (see [Appendix 2](#)). (revised per Amendments 02 and 03)

The study will consist of 2 phases: Prerandomization and Randomization. The Prerandomization Phase will last up to 30 days and consists of 1 visit during which subjects will be screened for eligibility. The Randomization Phase consists of a Treatment Period and a Follow-Up Period. The Treatment Period will last for a maximum of 52 weeks, with visits at Weeks 1, 5, 8, 12, 20, 28, 36, 44, and 52; the Follow-Up Period will extend from the End of Treatment (EOT) visit to the End of Study (EOS) visit.

Subjects who screen fail can be rescreened only once. All subjects will continue in the study until the 52-week evaluation is completed. Subjects who discontinue treatment prematurely will be followed up until study completion. All attempts will be made to capture height and weight in all subjects whether or not they are still on study drug at the end of the study. (revised per Amendments 03 and 04)

Study sites will be selected to ensure adequate representation of adolescents of ethnic and racial minorities. (revised per Amendment 03)

A Data Monitoring Committee (DMC) will be established to monitor and conduct periodic safety review of unblinded data. DMC members will be chosen based on their expertise in evaluating these clinical events. A separate DMC charter will be established. (revised per Amendment 03)

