Unless specified, for all other secondary efficacy endpoints, the continuous variables will be analyzed using mixed effect model repeated measurement analysis (MMRM) on the FAS for study treatment compared to placebo, as appropriate. The model will include all data and will include treatment, time, and the interaction of treatment by time as fixed effects, with adjustment for sex (male versus female), BMI and age at baseline, and subject as a random effect. (revised per Amendment 03)

Treatment by time interaction will be used to construct the treatment comparisons at a specific time. The MMRM model assumes that the missing data are missing at random and makes use of all available data even if a subject has missing data at some postbaseline visits. An unstructured covariance matrix will be used, and if the model fails to converge, then an autoregressive matrix will be used. (revised per Amendment 03)

Categorical variables will be analyzed using the Cochran Mantel Haenszel test, Chi-square test, or logistic regression as appropriate. Additional analysis may be performed as needed using appropriate statistical methodologies as specified in SAP.

Subgroup analyses will be performed on the primary efficacy endpoint, including sex (male and female), race (American Indian or Alaska Native, Asian, Black or African American, Native Hawaiian or other Pacific Islander, or White), and age. Additional subgroups may be explored, if deemed necessary. (revised per Amendment 03)

No adjustment for multiplicity is planned for other secondary endpoints, subgroup, and sensitivity analyses.

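### As written, the secondary MMRM gives sex, baseline BMI and age one coefficient for all visits, which can leave percentage change in BMI, and to a lesser degree waist, largely unadjusted at Week 52

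*Protocol*

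**What the plan says.** Protocol v10.0, section 9.7.1.6 (Other Secondary Efficacy Analyses), writes the MMRM out. Its mean model has "treatment, time, and the interaction of treatment by time as fixed effects, with adjustment for sex (male versus female), BMI and age at baseline"; the covariate clause in full is "adjustment for sex (male versus female), BMI and age at baseline, and subject as a random" effect. The Week 52 contrast comes from one term: "Treatment by time interaction will be used to construct the treatment comparisons at a specific time". On covariance: "An unstructured covariance matrix will be used, and if the model fails to converge, then an autoregressive matrix will be used". On missing data: "The MMRM model assumes that the missing data are missing at random". No covariate-by-time term is listed.

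Section 9.1 sets the treatment period "with visits at Weeks 1, 5, 8, 12, 20, 28, 36, 44, and 52". By the schedule in Table 2, height, weight and vital signs are taken at all nine of these visits. Waist is taken at Weeks 5, 12, 28, 36 and 52; glucose, insulin and HbA1c at Weeks 12, 28 and 52; lipids at Weeks 28 and 52; DEXA after baseline at Week 52 only.

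The primary analysis, in the same section, is an ANCOVA of change to Week 52 with sex as a factor and "the baseline age and BMI as covariates", so there the covariates get Week 52 coefficients. Section 9.7.2 assumes 40% dropout. Section 9.5.1.3 aims for the primary assessment in at least 80% of randomized subjects, on drug or not.

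**The concern.** Change from baseline starts at zero, so in growing adolescents the influence of age, sex and starting BMI on change in BMI or waist is likely to be small at Week 1 and larger at Week 52. A single coefficient cannot follow that. With an unstructured covariance the fit gives most weight to the visits with least variance, which for these outcomes are the earliest. The coefficient applied at Week 52 is then close to the Week 1 value.

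Two things are at stake. The Week 52 comparison loses precision that the covariates were listed to give. Also, a likelihood analysis under missing at random relies on a correct mean model. If the covariate-by-time effect is left out and dropout depends on a covariate differently in the two arms, the Week 52 difference is biased although the covariate is nominally in the model.

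**Working it through.** **1. The plan's own figures.** The documents give no figure for the MMRM. Section 9.7.2 supplies the inputs: 130 per arm, 40% dropout, SD 2.2 kg/m², difference 1 kg/m², two-sided 5%. Evaluable per arm: 130 × 0.6 = 78. Then √(78/2) × 1/2.2 = 2.84, 2.84 − 1.96 = 0.88, power 81%. This agrees with the stated 80% or more. The responder comparison (20% against 40%) gives 78.4%, also as stated.

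**2. Where the common coefficient settles.** With complete data it is a weighted mean of the visit-specific coefficients b:

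c = Σ wⱼbⱼ, with w = S⁻¹1 / (1′S⁻¹1), where S is the residual covariance.

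Assumptions, not in the documents: the covariate effect is 0.7 kg/m² per SD at Week 52, growing linearly from zero. It explains 0.49/4.84 = 10% of variance and leaves 4.84 − 0.49 = 4.35. For growing variance, a random walk has covariance 4.26 × (earlier week)/52 plus 0.09 on the diagonal; a random-slope form was also tried. For stable variance: equal variances, correlation 0.5.

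By hand for two visits (Weeks 28 and 52, random walk): the variances are 2.384 and 4.35 and the covariance is 2.294. The Week 28 weight is (4.35 − 2.294)/(2.384 + 4.35 − 4.588) = 0.958. The share kept is 0.958 × 28/52 + 0.042 × 1 = 56%.

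For the nine visits the same formula puts weights of about 0.82, 0.14, 0.03 and 0.01 on Weeks 1, 5, 8 and 12, and almost none later. The share kept is (0.82×1 + 0.14×5 + 0.03×8 + 0.01×12)/52 = 1.88/52, about 4%.

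With equal variances the weights are equal, so the share kept is the mean visit week divided by 52.

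| Visit schedule | Kept, growing variance | Kept, equal variance |
|---|---|---|
| Nine visits, Weeks 1-52 (percentage change in BMI; BP and heart rate) | 2-4% | 206/(9×52) = 44% |
| Waist, 5 visits | 4-11% | 133/(5×52) = 51% |
| Glucose, insulin, HbA1c, 3 visits | 9-25% | 92/(3×52) = 59% |
| Lipids, 2 visits | 27-56% | 80/(2×52) = 77% |
| DEXA, 1 visit | 100% | 100% |

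The growing-variance column is the relevant one for percentage change in BMI and waist; the equal-variance column is nearer to blood pressure and heart rate. If the covariate effect grows as the square root of time, about 14-33% is kept for percentage change in BMI and waist. If it is constant over visits, 100% is kept and there is no problem.

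**3. Precision.** If a share k is kept, Week 52 residual variance rises by (1 − k)² × R²/(1 − R²). At k = 0.04 and R² = 10%: 0.92 × 0.111 = 10%, or a residual SD of 2.19 instead of 2.09. At R² = 5% it is 5%. At R² = 20% it is 20% for waist (k = 0.11) and 23% for percentage change in BMI. In simulated trials the variance of the Week 52 difference was 4, 9 and 17% larger at R² of 5, 10 and 20%.

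**4. Bias.** Large-sample maximum-likelihood fits with unstructured covariance, growing variance, a true difference of −1 kg/m² and 40% dropout that is never retrieved, at 0.7 kg/m² per SD:

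- Dropout log-odds shifted by 0.7 per SD in one arm only: bias −0.04 (late dropout) to −0.16 (early dropout).
- Opposite shifts in the two arms: −0.04 to −0.30.
- The same shift in both arms, or no dependence: about 0.
- Covariate-by-visit terms added: within ±0.045 in every case, which is simulation noise.

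On the percentage scale (assumed SD 6 points, difference −2.8 points, shift 0.5 per SD, R² 5-20%), the bias is roughly 5-20% of the effect without retrieval. With half the dropouts measured at Week 52 it is 0.06-0.10 points for one-arm dependence (2-4% of 2.8) and 0.11-0.21 for opposite shifts (4-8%), so roughly 3-8% overall. Reversing the shift reverses the sign.

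**The case against.** The model text says only that there is adjustment for these covariates, and section 9.7.1 leaves further detail to the SAP, which may already contain the interactions. That is fair, but the protocol spells out the fixed effects, names one interaction, and fixes the covariance and its fallback. A reader would fit main effects. If the SAP already has the terms, only the protocol wording needs aligning.

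The size rests on inputs the documents do not give: how covariate effects develop over visits, how much variance they explain, and arm-specific dropout. That stands, and the figures are conditional on it.

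A reader might take the 40% dropout as the share missing at Week 52. The documents do not support that. Sections 9.1 and 9.5.5 keep subjects who stop drug in follow-up and call for all attempts to capture their height and weight, and section 9.5.1.3 aims for at least 80% assessed. The smaller bias, with retrieval, is therefore the more relevant figure for percentage change in BMI.

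A reader might also infer that the treatment effect would be overstated. Nothing in the plan fixes the sign: it follows from which subjects leave which arm.

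Finally, these endpoints carry no multiplicity control, and the primary and key secondary analyses use other models. This limits the consequence.

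**Conclusion.** The point holds as a cheap improvement for percentage change in BMI and, to a lesser degree, waist circumference. If covariate effects and variance both grow over the year, the model as written keeps about 2-10% of the Week 52 covariate effect (about 14-33% under square-root growth). The near-certain cost under those assumptions is precision: Week 52 residual variance about 5-20% larger for covariates explaining 5-20%. Bias is only a possibility. It needs dropout that depends on the covariates differently by arm, can go either way, and is roughly 5-20% of the effect without retrieval or 3-8% with half retrieved. With complete data or equal dependence in both arms it is about nil.

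It would be wrong to conclude that every secondary endpoint is barely adjusted at Week 52. Blood pressure and heart rate keep about 44% under equal variances, glucose measures and lipids keep more than percentage change in BMI under either variance pattern, and DEXA has a single post-baseline visit. A smaller loss of adjustment does not by itself rule out bias there if a covariate effect were to grow as strongly, but the documents give no ground to expect that. Nor does the point weaken the Week 52 ANCOVA or the responder analysis.

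**What to change.** In section 9.7.1.6, extend the MMRM fixed effects to treatment, visit, treatment-by-visit, sex, baseline BMI, baseline age, and the interactions of sex, baseline BMI and age with visit. Do this at least for percentage change in BMI and waist circumference. The Week 52 comparison is then adjusted with Week 52 coefficients, as in the primary ANCOVA.

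The cost is one sentence and some extra parameters: 3 covariates × 8 further visits = 24 at most, 3 × 4 = 12 for waist, 6 for glucose measures and 3 for lipids. That is small for about 260 subjects. For small subsets such as subjects with T2DM, whose number is not stated, the text can allow main effects only if the fuller model does not converge. If the covariate effects turn out constant over visits, the added terms do no harm beyond those parameters.
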